**Focus Groups and Usability Testing:** Twenty high-risk adolescents will be recruited to participate as test users in the development phase to give us initial reactions to mockup of modules, and a subgroup of 10 of these participants will be recruited to participate in preliminary usability testing of the modules. Feedback from usability testing will be used to inform adaptations to the app. The prototype app will then be evaluated in an efficacy trial with 380 additional high-risk adolescents. The primary outcomes of the evaluation-testing phase will be changes in adolescent substance use attitudes and behaviors and emotion regulation measured at three time points: baseline, 4 weeks post- baseline (end of treatment), and three months post-baseline. The proposed efficacy trial will evaluate the extent that the Qlarity app influences positive behavior change and will provide power estimates for later larger scale evaluation.

**Efficacy Trial:** Based on our power calculations, we will recruit 380 adolescents who are involved in the juvenile justice system. We have a long history of cooperation with the DHS and have well-established recruitment procedures. Eligible adolescents and their consenting parents will be recruited on a continual basis and will be included in the study for 3 months post-baseline. The participants will be randomly and equally assigned to the Qlarity condition ( $n = 190$ ) or the DC standard treatment condition ( $n = 190$ ) following adolescent assent and parent consent. Given that all youth will be involved in the juvenile justice system, we will assess all services offered and accessed by youth in both conditions.

Based on our prior experience, we expect many of the youth to be under orders to be participating in urine screening or other intervention services through DHS. Data from our current and prior studies with this population suggest that despite receiving random urine screens as part of their probationary status, 90% of youth are involved in ongoing alcohol, tobacco or other drug use (79% alcohol; 68% tobacco; 81% marijuana, and 53% other drug; 90% positive for one or more substance) at the time of referral. We will track additional services, including mandated urine screens, via official DHS reports and using a services utilization measure at each follow-up time point.

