**Main-effects analyses.** Tests of the general effectiveness of the Qlarity app within this three-panel (pretest, 1- month, and 3-month follow-up) randomized trial requires an analysis that accounts for the dependence of multiple assessments nested within participants that were assigned to conditions. Thus, we will test most of our research hypotheses with random effects growth models within the hierarchical and structural equation modeling (SEM) frameworks with individual variability in change in study outcomes from pretest to 3-months nested within individuals. Following Singer and Willet when constructing the longitudinal model, we will (a) examine empirical growth plots; (b) fit an unconditional means model; (c) fit an unconditional linear growth model; (d) fit unconditional non-linear models; and (e) compare models of longitudinal change from the previous two steps using the Akaike Information Criterion. Individual variability change in the outcomes from baseline to the 3-month follow-up assessment will be modeled as a function of intervention condition. Intervention condition by time interactions will test whether groups differ on individual trajectories over the course of the study period. We will also use logistic regression models reporting odds ratios (OR) to test for differential rates of abstinence at the 3-month follow-up assessments with intervention condition a two-level predictor.

**Moderator effects.** Moderating effects of demographics (gender and minority status) and number of baseline offenses will be explored by adding the moderator to the random effects growth models described above. The multiplicative interaction term between the participant level moderators constitute a three-way cross-level interaction with time in the growth models and addresses whether the level of the baseline moderator impacted the magnitude of intervention condition on change in the outcome. All significant cross-level interactions will be probed by computing sample-estimated intercepts and slopes of the trajectories of the outcomes at conditional levels of the moderator, separately, within the Qlarity and usual care group (i.e., simple trajectories) using methods described by Curran (Curran, Bauer et al. 2006).

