**Power considerations.** The assumptions for the power estimates include a sample size of 380 participants, Type II error rate of 20% ( $\beta = .20$ ) and a 2-tailed alpha = .05. Power estimates for multilevel growth models require assumptions that are not easily established in longitudinal studies (e.g., complete data, homogeneous random-effects covariance structures within conditions). Thus we rely on the fact that power for multilevel growth models has been shown to surpass that of the mixed-model ANCOVA. The proposed growth models, then, will detect smaller differences between conditions than the ANCOVA models on which power estimates were based. Allowing for intent-to-treat analyses that makes use of all available data using missing data techniques described above and a pretest covariate  $r^2 = .25$ , there is sufficient power to detect main effects for condition of Cohen's  $d = .25$  (small effect size) and detect condition by moderator effects of  $d = .35$  (small to medium effect). The smallest subsample expected for decomposition of significant moderating effects is approximately 150 minority participants (75 per condition) which will provide sufficient power ( $>.80$ ) to detect condition effects of  $d = .40$  (medium effect). The study is also powered to detect small to medium between condition effect size differences (ORs = 2.05 – 2.25) for the logistic regression models predicting an estimated 15-20% substance use abstinence rates at follow-up. Using mediation effect size guidelines from Kenny for a model containing a dichotomous independent variable and a continuous mediator, effect sizes of .02, .15, and .40 derived from the product of  $d$  and  $r$ , represent small, medium, and large effect sizes respectively. Assuming small to moderate effects for the indirect pathway ( $r = .20$ ), the proposed sample size has sufficient power ( $>.94$ ) to detect small effect sizes or greater ( $dr = .04$ ) for tests of mediation. Process analyses involving correlation coefficients will have adequate power to detect small to medium effects ( $r = .20$ ).

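### Significant moderators are to be probed by slopes within each arm, with no stated estimate or interval for the Qlarity-minus-DC difference that the power section assumes for the same step

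*Combined protocol and SAP*

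**What the plan says.** Under Data Analysis, the Moderator effects paragraph adds gender, minority status and number of baseline offences to the growth models as moderators. It tests each through a three-way interaction with condition and time. Where that term is significant, the follow-up step computes intercepts and slopes at chosen values of the moderator, "separately, within the Qlarity and usual care group (i.e., simple trajectories"), and cites a published probing method. No comparison of the two arms' slopes at a given moderator value is named.

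The Power considerations paragraph describes the same step differently: "The smallest subsample expected for decomposition of significant moderating effects is approximately 150 minority participants (75 per condition"). For that subsample it claims power above .80 to detect condition effects of d = .40.

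For the main effects, by contrast, the plan does name the between-arm test, as the condition-by-time interaction.

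**The concern.** A moderator analysis asks in whom the app adds something over DC (usual services). A slope within the Qlarity arm does not answer that. It combines any app effect with whatever all participants share. Stage 2, Study Design, has every participant instructed to try to cut down, and the Overview of the Proposed Intervention Conditions leaves usual services untouched in both arms. Some improvement common to both arms is therefore plausible.

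If the reported follow-up is one slope and p-value per arm, readers will tend to compare the p-values: significant in one arm, not in the other. That comparison can suggest a subgroup effect where none exists, or miss a real one when both arms improve. The plan does not rule it out. Feasibility benchmark (a) already counts significant pre-post gains without naming a comparator, although benchmark (b) is comparative.

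At stake are the subgroup statements only, not the main-effects inference.

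**Working it through.** **Inputs from the documents.** Under Power considerations: "The assumptions for the power estimates include a sample size of 380 participants", "a 2-tailed alpha = .05", "Type II error rate of 20" per cent, pretest covariate r² = .25, and 75 minority youth per condition with d = .40. Under Stage 2, Efficacy Trial: equal allocation, 190 per arm. The other youth then number 190 − 75 = 115 per arm.

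**Step 1: which quantity the plan powers.** Take a between-arm ANCOVA comparison in the minority subgroup.

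- Residual SD = √(1 − .25) = .866.
- SE = .866 × √(2/75) = .1414.
- .40/.1414 = 2.83, so power = Φ(2.83 − 1.96) = .807 (.802 with the noncentral t).

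This matches the stated figure of more than .80. Without the covariate, power is .688. The same formula with 190 per arm and d = .25 gives .803, which matches the main-effect claim. The powered subgroup quantity is therefore a Qlarity-versus-DC contrast.

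**Step 2: what within-arm tests do with no app effect.** Assume a pre-post correlation of .5 (from r² = .25), so the SD of change is √(2 × (1 − .5)) = 1. Let both arms of 75 truly change by .35.

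- Each arm: z = .35 × √75 = 3.03, power = Φ(3.03 − 1.96) = .858.
- Exactly one arm significant: 2 × .858 × .142 = .244.
- Both significant: .858² = .736.
- Simulation gives .255 and .722, while the between-arm test rejects in 4.8%.

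**Step 3: what they do with a real effect.** Let the true changes be .75 (Qlarity) and .35 (DC), a difference of .40. Both arms are significant in 85% of simulated trials, so the pattern of p-values does not show the difference. The between-arm test on change scores detects it in 69%. ANCOVA would do better, as in step 1.

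**Step 4: the plan's actual sequence, probing only after a significant interaction.** Assume an app effect of zero in minority youth and .50 in others, and an SD of change of 1. The interaction SE is √(2/75 + 2/115) = .210, so the interaction is significant in about Φ(.50/.210 − 1.96) = .66 of trials. Among those trials, by simulation, a significant improvement in the minority slope occurs as follows:

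| Improvement shared by both arms | Qlarity | DC | Exactly one arm | Qlarity only |
|---|---|---|---|---|
| .15 | 15% | 34% | 35% | 7.6% |
| .25 | 46% | 71% | 45% | 10.4% |
| .35 | 80% | 94% | 22% | 4.3% |

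In the same trials the between-arm minority contrast is significantly positive in about 0.07% and significantly negative in about 3.8%, with a mean of about −.07 although the truth is zero. Before selection, each side would be 2.5%. Part of the gap between the within-arm and between-arm rates therefore comes from conditioning on a significant interaction.

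**The case against.** The strongest reply is that the between-arm question is already in the plan. The three-way term is itself a between-arm test, and probing follows only when it is significant. Trajectories are computed in both arms at the same moderator values, so subtracting the two slopes gives the point estimate of the Qlarity effect at that value. The power paragraph shows that subgroup condition effects are intended. The cited probing method may include tests between trajectories, which cannot be checked from the documents. The moderator analyses are also described as exploratory.

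Most of this stands. A reader might infer that the method cannot yield the Qlarity effect in a subgroup, or that the randomised comparison is lost. The documents do not support either reading: the estimate is recoverable, and what is missing is its stated standard error, interval and role in the conclusions. Nor does the plan say that subgroup claims will rest on one arm's slope.

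A reader might also take the 80% figure for the Qlarity slope alone as the rate of false app claims. It is not. The DC slope is reported beside it and is significant in 94% of the same trials; the Qlarity-only pattern occurs in 4.3%.

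What does not fall away is the mismatch between the two paragraphs. One makes a formal power claim for a contrast that the other, describing the same step, does not name.

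**Conclusion.** The point holds as an inconsistency with a better method readily available; it is not a failure of the design. The probing rule names only within-arm quantities, while the power section assumes a between-arm subgroup effect (power .81 at d = .40, 75 per arm). Relying on significance by arm would be unsafe: with no app effect in minority youth, the two arms disagree in roughly 22% to 45% of trials with a significant interaction. Most of those disagreements show improvement in DC only; Qlarity only accounts for about 4% to 10%.

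These rates rest on assumptions that the documents do not give: an SD of change of 1, app effects of zero and .50 in the two groups, and shared improvement of .15 to .35. The direction of the argument does not depend on them. Because the analyses are exploratory and the point estimate is recoverable, this should be corrected but does not threaten the main-effects inference.

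**What to change.** In the Moderator effects paragraph, state that:

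- for each significant interaction, the Qlarity-minus-DC difference in change is estimated from the fitted three-way model at each moderator level (each gender, each minority group, low and high offence counts), with a 95% CI;
- subgroup statements rest on those differences and are labelled exploratory, because they follow selection on a significant interaction and are biased by it, as step 4 shows;
- the within-arm simple trajectories are kept as description and plots.

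The cost is a sentence or two. The contrasts come from a model already planned, no sample size or power figure changes, and the paragraph then agrees with Power considerations. The change does not remove the selection bias, hence the exploratory label.

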## Data Collection Procedures

**Overview and timeline for the proposed data collection:** In the proposed study, a total of at least 380 youth will be recruited and baseline assessed for the study. We anticipate that approximately 10% of these will fail to complete the study, resulting in a sample of at least 342 youth with complete data and an intent-to-treat analysis strategy which will include all 380 youth. We will conduct baseline assessments and follow-up assessments at treatment completion (1 month), and at 3 month post-baseline.

**Assessments:** The *baseline assessment* primarily measures youth risk factors, as well as past and current substance use, and will consist of an in-person interview including questionnaires with the youth.

The *treatment completion (1-month), and 3-month assessments* are aimed at assessing short and longer term outcomes and will consist of two components: (a) an in-person interview and questionnaires with the youth, and (b) usability and satisfaction ratings for the Qlarity app. Because every participant has unique needs, we have standardized guidelines that allow for minor modifications to our procedures when needed. For example, staff will read aloud questionnaires for participants who are nonreaders, and computer-assisted questionnaires will be available in hardcopy format. We will travel to participant residences or other locations to conduct the interviews as needed.

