**Measures:** The following measures will be used to examine baseline demographic and pre- and post-changes in mindfulness skills, emotion regulation, and substance use: 1) Demographics, 2) Alcohol and Drug Use Survey, 3) Cigarette Use, 4) Adolescent Attitudes Questionnaire, 5) Emotion Regulation Scale, 6) Five Facet Mindfulness Questionnaire, 7) Youth Substance Use Interview (including Services Utilization), and 8) Qlarity usability and satisfaction rating. The Alcohol and Drug Use Survey is a 48-item scale that combines the Michigan Alcohol Screening Test (MAST) and the Drug Abuse Screening Test (DAST) and the Self-Efficacy for Limiting Substance Use. These scales are widely used as measures to assess the level and frequency of alcohol and drug use, use of mindfulness skills, as well as the ability to limit substance use, and have been shown to have good psychometric properties. In addition, urinary drug tests will be conducted at the baseline, 1- and 3-month follow ups. UA results will be photocopied after completion, and the UA cups will be discarded immediately; no identifying information will be recorded on the UA cups. We will use the same UA drug testing procedure that we have found to be successful in our current NIH funded study with adolescents in the juvenile justice system. All data will immediately be moved to a secure, locked location within ORI/Influents Innovations accessible only to the PI and research staff. The Services Utilization Survey is an interviewer-administered instrument that collects information about a respondent's use of a wide range of services such as in- and out-patient medical care (hospital, clinic, or office based), mental health treatment, drug and alcohol abuse treatment, and

Table 1. Measures		Assessments		
Measure	Baseline	1 Month	3 Month	
Adolescent Attitudes Questionnaire	●	●	●	
Alcohol and Drug Use Survey (MAST/DAST)	●	●	●	
Qlarity Usability and Satisfaction		●	●	
Cigarette Use	●	●	●	
Demographics	●			
Emotion Regulation Scale	●	●	●	
Five Facet Mindfulness	●	●	●	
Urine Drug Screens	●	●	●	
Youth Substance Use Interview (Services Utilization)	●	●	●	

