**Mediation effects.** Growth-curve models implemented in an SEM framework will be used to explore whether observed condition effects on tobacco, alcohol, and drug use are mediated by adolescent attitudes and mindfulness. Following Preacher et al., models will be constructed by individually fitting growth models for mediators and outcomes using the growth curve model-building sequence described above to develop the best longitudinal change model. Then mediator and outcome growth curves will be combined in a single model. We will test whether (a) condition predicts change in each mediator, (b) condition predicts change in each outcome, (c) mediator change predicts outcome change, and (d) the condition effect on the outcome is significantly weaker when controlling for level or change in the mediator. Significance of indirect effects will be tested using bias-corrected bootstrapped confidence intervals.

**Process analyses.** A critical element to the program evaluation is the acceptability of the intervention to the target population, which will be assessed via rate of attrition, level of program

use, and degree of program satisfaction. Dose-response analyses will be conducted to examine the degree to which treatment engagement and retention (e.g., frequency and duration of app use, number of modules completed) predict change in the outcome measures at the post-intervention and follow-up assessments. Canonical correlation analyses will be used to examine the association between the dosage measures and outcome measures within the Qlarity condition. We will also test the hypothesis that those participants who report greater satisfaction with the intervention will have greater improvement in baseline-post scores using residual gain score analyses. Lastly, treating participant satisfaction as a process variable, we will examine the correlations between the satisfaction ratings and the amount of treatment engagement/retention.

**Missing data.** Missing data in outcome measures may result from dropout or item non-response. The mixed- growth models described above make use of maximum likelihood estimates and allow for use of all available outcome data from all assessments, reducing bias and increasing power. In general, maximum likelihood procedures, as well as imputation methods, will be used as they can provide unbiased estimates even in instances of substantial attrition. Multiple imputation procedures will follow best-practice recommendations.

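### The satisfaction hypothesis should be tested by one regression on baseline and satisfaction rather than by residual gain scores, and the result described as an association

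*Combined protocol and SAP*

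**What the plan says.** The Process analyses paragraph of Data Analysis states the hypothesis and the method: participants reporting "greater satisfaction with the intervention will have greater improvement in baseline-post scores using residual gain score analyses". It gives no model equation and does not say whether the 1-month or the 3-month rating is used. It goes on to examine correlations with engagement, "treating participant satisfaction as a process variable".

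The post visit can be identified. The same paragraph has engagement measures "predict change in the outcome measures at the post-intervention and follow-up assessments", so post-intervention and follow-up are different visits. Stage 2, under Focus Groups and Usability Testing, places the later assessments at "4 weeks post- baseline (end of treatment), and three months post-baseline". Post is therefore the 1-month visit.

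Data Collection Procedures, under Assessments, schedules "b) usability and satisfaction ratings for the Qlarity app" at the 1-month and 3-month visits, alongside the outcome interview and questionnaires. The Table 1 row for "Qlarity usability and satisfaction" is marked at those two visits and not at baseline.

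Power considerations says: "Process analyses involving correlation coefficients will have adequate power to detect small to medium effects", with r = .20. The general assumptions there are a Type II error rate of 20% and "2-tailed alpha = .05".

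**The concern.** A residual gain analysis usually has two steps: regress the post score on the baseline score, then relate the residual to the predictor. The second step leaves in satisfaction whatever part of it is explained by baseline. That part cannot correlate with the residual, so it only dilutes the slope. A youth's starting level of use, emotion regulation or mindfulness could plausibly colour how the app is rated, so a non-zero correlation cannot be ruled out.

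Separately, no rating precedes the post score. A youth who has already improved by 1 month may rate the app higher for that reason. At stake are an understated association and some loss of power in a secondary analysis, and a result that could be over-read when the app is developed further.

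**Working it through.** **Inputs.** Qlarity arm n = 190 (Efficacy Trial). About 10% not completing (Data Collection Procedures), so 190 × 0.9 = 171. Target r = .20, two-sided alpha .05, power .80 (Power considerations). The satisfaction-baseline correlation rho is not given, so it is an assumption and is varied. The Qlarity arm is used because only those youths have the app to rate.

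**1. The plan's own figure.** Power = Φ(atanh(r)·√(n − 3) − 1.96), with atanh(.20) = 0.2027.
- n = 190: 0.2027 × √187 = 2.772; 2.772 − 1.960 = 0.812; power .792 (noncentral t: .799).
- n = 171: 0.2027 × √168 = 2.628; 2.628 − 1.960 = 0.668; power .748 (noncentral t: .756).

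The claim of adequate power at r = .20 is reproduced with all 190 youths. After the plan's own dropout, power is about .75.

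**2. Shrinkage.** Let baseline X and satisfaction S be standardised with correlation rho, and let Y = γX + βS + e.
- Step one: Y on X has slope γ + β·rho, leaving the residual β(S − rho·X) + e.
- Step two: the covariance of S with S − rho·X is 1 − rho². The slope on S is therefore β(1 − rho²).
- The correlation of the residual with S is the partial r × √(1 − rho²).
- With no association, the two-step test rejects with probability 2[1 − Φ(1.96/√(1 − rho²))].
- One regression of Y on X and S returns β at any rho.

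The sign of rho does not matter. At a true partial r of .20, the formulas give:

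| rho | slope kept | residual-S correlation | two-step power, n = 171 | one-regression power, n = 171 | two-step power, n = 190 | one-regression power, n = 190 | two-step type I error |
|---|---|---|---|---|---|---|---|
| 0 | 1.00 | .200 | .748 | .745 | .792 | .790 | .050 |
| .1 | .99 | .199 | .744 | .745 | .788 | .790 | .049 |
| .3 | .91 | .191 | .707 | .745 | .752 | .790 | .040 |
| .5 | .75 | .173 | .621 | .745 | .667 | .790 | .024 |

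**3. Simulation check** (10,000 trials per setting, n = 171).
- rho = 0: the two methods agree, both with power .751.
- rho = .3: slope ratio .906; power .714 against .747, a loss of 3.3 points (formula: 3.9).
- rho = .5: slope ratio .747; power .635 against .750, a loss of 11.5 points (formula: 12.4).
- Two-step type I error: .041 at rho = .3 and .025 at rho = .5. For one regression it was about .05 throughout.

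**4. Order of measurement.** The earliest rating and the post score come from the same visit, and the 3-month rating comes after it. Neither rating can show that satisfaction preceded the improvement being analysed.

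**The case against.** **The shrinkage is conditional.** The plan gives no equation. If the team means a regression of post on baseline and satisfaction together, there is no shrinkage. No rho is given either, and the larger losses need a rho near .5, which nothing in the documents supports. Any error is conservative. Up to rho = .3, the drop due to dropout (.792 to .748, or 4.4 points) is at least as large as the loss due to the method. The r = .20 power statement covers process correlations in general and not this test in particular. All of this stands, and it keeps the point small.

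**The plan does not claim time order.** A reader might infer that the test will falsely confirm that satisfaction leads to later benefit: if improvement raises ratings by r = .1, .2 or .3, the same-visit test is significant in about 25%, 75% or 98% of trials. These are not error rates for the stated hypothesis. They are the power of a correlation test at n = 171 to detect an association that is really there; the .748 in the working is the middle case. The plan says only that more satisfied youths improve more. What remains is a limit on interpretation, not a contradiction.

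**A lagged model is not a substitute.** A reader might also infer that the 3-month score, regressed on 1-month satisfaction given the baseline and 1-month scores, should replace the planned test. It asks a different question. If the association with improvement arises wholly by 1 month, with nothing further afterwards, satisfaction has no remaining coefficient in that model. A simulation of this case (n = 171, partial r = .20, assumed correlations of .5 from baseline to 1 month and .7 from 1 to 3 months) found the planned test significant in 75% of trials and the lagged model in 5%. Treatment ends at 4 weeks, so the case is plausible.

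**Conclusion.** The point holds as a low-cost improvement to a secondary, within-arm analysis. Read in the ordinary two-step way, the method multiplies the satisfaction slope by (1 - rho squared) and makes the test conservative. The size depends wholly on an unstated rho: nothing at 0, modest at .3, material at .5. These figures assume linear relations, a true partial correlation of .20 and 171 completers. One regression removes the shrinkage and has no practical drawback in the runs.

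The same-visit rating limits what a positive result means; it does not make the stated test invalid. The documents do not support reading this as an inflated false-positive rate or as a threat to the randomized comparison. The feasibility benchmarks use mean satisfaction and not this association, so they are not affected.

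**What to change.** In Data Analysis, Process analyses, replace the reference to residual gain scores with wording such as: *Within the Qlarity arm, the 1-month score will be regressed on the baseline score and the 1-month satisfaction rating. The satisfaction slope will be reported with its 95% CI. Because the rating and the 1-month score come from the same visit, the result will be described as an association that does not show which came first.* If a single regression was always intended, this wording makes that clear.

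A model of the 3-month score on 1-month satisfaction, given the baseline and 1-month scores, may be added as an exploratory analysis of change after 1 month. It should not replace the stated test.

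The cost is wording and a few lines of code, with no new data or visits. The extra covariate uses one degree of freedom, which by the formula costs about 0.3 points of power at n = 171 when rho is 0 (.748 to .745).

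### The 80% power for a main effect of d = .25 is an ANCOVA figure with no loss; at the 342 youth the plan expects to complete, the same calculation gives about .76

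*Combined protocol and SAP*

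**What the plan says.** Under Data Analysis, the paragraph on power considerations gives its basis: "The assumptions for the power estimates include a sample size of 380 participants", a "Type II error rate of 20" percent and "2-tailed alpha = .05". It says that the estimates come from ANCOVA models with a pretest covariate r² of .25, and that the planned growth models will do better than ANCOVA. It claims:

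- sufficient power for a main effect of d = .25;
- for decomposing moderator effects, a smallest subsample of "approximately 150 minority participants (75 per condition) which will provide sufficient power", above .80, at d = .40;
- for correlations, "Process analyses involving correlation coefficients will have adequate power to detect small to medium effects", given as r = .20, with no sample size and no numeric power.

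The paragraph enters no dropout figure. It refers instead to intent-to-treat analysis using all available data.

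Data Collection Procedures expects about 10% of youth not to complete, "resulting in a sample of at least 342 youth with complete data", with all 380 kept in the intent-to-treat analysis. The process analyses paragraph examines the "association between the dosage measures and outcome measures within the Qlarity condition". Stage 2 allocates 190 youth to each arm. The statistical design and power overview repeats the expectation of detecting 0.25 standard deviations.

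**The concern.** The power paragraph counts every enrolled youth, while the data collection section expects to lose about one in ten. Keeping dropouts in an intent-to-treat analysis addresses bias and uses what they did provide; it does not supply the outcomes they never gave. If the stated power is met only at full enrolment, any loss takes it below the plan's own target unless some other gain offsets it, and the plan puts no number on such a gain.

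The stake is modest. Overstated sensitivity makes it easier to read a null main-effect, subgroup or dose-response result as evidence of no effect. The trial is also meant to inform power for a later, larger evaluation, so its own power statement should be traceable.

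**Working it through.** **Inputs.** From the power paragraph: N = 380, two-sided alpha .05, target power .80, r² = .25, d = .25 (main), d = .40 with 75 per arm (minority subgroup), r = .20 (correlations). From Stage 2: 190 per arm. From Data Collection Procedures: about 10% loss, so 380 × .90 = 342, or 171 per arm if loss is equal. The same loss applied to 150 gives 135, or 67.5 per arm.

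**Formula for the ANCOVA figures.** Non-central t with 2n − 3 degrees of freedom and non-centrality d/√(1 − r²) × √(n/2), where n is the number per arm and √(1 − .25) = .866.

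**Step 1: reproduce the plan at full enrolment.**
- Main effect: (.25/.866) × √(190/2) = 2.814, power .801. At 189 per arm it is .799.
- Subgroup: (.40/.866) × √(75/2) = 2.828, power .802. At 74 per arm it is .797.

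Both claims reproduce, and both sit at the smallest sample that reaches .80.

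**Step 2: apply the plan's own loss.**
- Main effect: (.25/.866) × √(171/2) = 2.669, power .759. Detectable d at .80 power is .263.
- Subgroup, if 150 is counted before loss: (.40/.866) × √(67.5/2) = 2.683, power .759. Detectable d is .42.
- Subgroup, if 150 is counted after loss: .802, as in step 1.

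The normal approximation gives .761 and .765 in place of the two values of .759.

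**Step 3: what partial follow-up recovers.** The documents give no correlation between follow-ups, so I assume ρ = .5 to .8 between month 1 and month 3, with each correlated .5 with baseline (this is r² = .25). The partial correlation is c = (ρ − .25)/.75. If m youth per arm have month-1 data and 171 have month-3 data, the variance of the month-3 effect is 2 × .75 × [(1 − c²)/171 + c²/m].
- No dropout has month-1 data (m = 171): .761.
- Half to all dropouts have month-1 data (m = 180.5 to 190): .763 to .784 for the main effect. The same calculation gives .768 to .788 for the subgroup.

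All of these remain below .80.

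**Step 4: what the growth model might add at 171 per arm.** I use the same assumed correlations, d = .25 at month 3 and an effect that grows linearly, estimated by generalised least squares.
- Arms constrained to a common baseline: about .76 (ρ = .5) to .87 (ρ = .8), reaching .80 near ρ = .7.
- Condition-by-time slope with free intercepts: about .65 to .83 over the same range.

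The sign of the difference from ANCOVA therefore depends on model form and on correlations that the plan does not state.

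**Step 5: process correlations.** Fisher z: power = Φ(atanh(.20) × √(n − 3) − 1.960), with atanh(.20) = .2027.
- n = 190: 2.772 − 1.960 = .812, power .792 (a t-based version gives .799).
- n = 171: 2.628 − 1.960 = .668, power .748. Detectable r is tanh(2.802/√168) = .213.

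**The case against.** The strongest reply is that .76 describes an analysis the plan will not run. The planned model uses three assessments, and the plan presents ANCOVA as a conservative base. This part stands: a reader might infer that the trial's actual power is .75 to .76, and the documents do not support that. Step 4 shows that it could be above or below .80. By the same token, the plan cannot lean on a gain it has not calculated. Its own text says that growth-model power needs assumptions that are hard to establish, and names complete data among them.

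Second, a reader might infer that the above-.80 subgroup claim is simply false. The plan calls 150 the smallest subsample expected for the decomposition, which could mean youth analysed. Because the section starts from 380 enrolled, counting before loss is the more natural reading, but it is not stated.

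Third, a reader might infer that the correlations were wrongly powered on 380. The plan gives no n there. At 380, power for r = .20 would be .976, whereas r = .20 is close to what 190 can detect at .80, so the figure looks like one for the Qlarity arm. The plan says only that power is adequate, and .75 to .79 does not contradict a stated number. Dosage also comes from login tracking, which a missed interview does not by itself remove.

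Finally, 342 is a floor for complete data, not a count of month-3 outcomes; a youth who misses only month 1 still contributes at month 3. The shifts (.25 to .26, .40 to .42, .20 to .21) are small. Both points limit the size of the problem but do not reconcile the two sections.

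**Conclusion.** The main-effect statement holds on its declared ANCOVA basis only if no one is lost. With the loss the plan itself expects, that basis gives about .76 at d = .25, or .80 at d of about .26: a shortfall of about 4 points. This assumes equal loss across arms and 171 month-3 outcomes per arm. Partial follow-up data, under the correlations assumed in step 3, bring it to .784 at most. The effect of the growth model is unknown from the documents.

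The subgroup figure is conditional: about .76 if the 150 are counted before loss, .80 if after. The process correlations call for clarification rather than correction. The 0.25 standard deviation statement in the overview names no power level, so it needs alignment only. The point is minor, and neither the design nor the analysis has to change.

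**What to change.** 1. In the power paragraph, state the ANCOVA power on expected completers: d = .26 at 342, or power .76 at d = .25. Align the 0.25 standard deviation statement in the statistical design and power overview.
2. Say whether the 150 minority participants are counted before or after loss. If before, give a detectable d of .42, or power .76 at d = .40.
3. State that the dosage-outcome correlations use the Qlarity arm only, with n of about 171 and a detectable r of about .21.
4. If credit is taken for the growth model or for partial follow-up, give the assumed correlations, the model form and the resulting power.

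The cost is a few sentences and slightly less favourable figures, with no extra enrolment. Only if the sponsor wished to keep .80 at d = .25 on the ANCOVA basis after 10% loss would enrolment have to rise, to 380/.90, or about 423.
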